5.7 Precautions Taken for Web-BasedAccess

All paper research records will be stored in locked file cabinets and will be accessible only to research personnel. All electronic research records will be computer password protected and accessible only to research personnel. All research records will be transmitted to CCISC, will be labeled with a code, and will not contain any identifiable information about the subjects. A m a s t e r

key/list which links with the subject's PHI, such as the patient's name with the code on the research records and specimens will be maintained at individual participating institutions. Information about any subject's participation in this study or the results of procedures performed in this study will be placed in the subjects' medical record; as such, this information could be made available to your employer or insurer. While individual details about a particular case might be provided in publications or presentations, they will not be discussed in a way that would allow any subject to be individually identified as a participant.

Protecting data and patient privacy is of great importance to this study. All research records will be saved in a password protected computer at individual participating centers. Access to the records will be limited to research personnel alone. Anti-virus software will be used to protect every computer network. Several different hardware and software solutions will be used to ensure that unauthorized users cannot access our computer systems. Data Encryption will be used that transposes the PHI which is sent from each participating sited to our server and browser into a code that cannot be understood or altered without using a "key". The "key" deciphers the information from our server to be able to display on any browser. Data transmitted between participating sites will be protected using Message Authentication Codes (MACs). The MAC will be based on the actual data itself, and provides a quick way to verify that the data wasn't changed or tampered with in route.

6 Study Completion

Subject participation in the clinical investigation will conclude upon completion of the follow-up visit at 6 months' post device implantation procedure. If a subject misses the scheduled follow-up visit within the 6-month window, the subject will be considered as having missed the visit (which will be deemed a deviation from the clinical study protocol and the applicable form will be completed).

A subject will be considered 'Lost to Follow-up' after two missed scheduled visits within the 6month window, a minimum of two unsuccessful phone calls from investigational site personnel to the subject. These two phone calls must be documented in the subject's research records. If the subject is deemed lost to follow-up, a certified letter will be sent to the subject's last known address or to the subject's general practitioner (GP). A copy of the letter must be maintained in the subject's research records.

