7.4 Analysis Population

The analysis of the primary and secondary endpoints will include all subjects who achieve a successful implant, which is defined as leaving the catheterization lab with a device implanted in the PDA. If a subject has multiple devices attempted during the same procedure, but leaves procedure with at least one device within the PDA the procedure is considered successful. Subjects without an implanted device in the PDA will be excluded. Additionally, subjects who had no follow- up visits up to the six-months +/- one-month window, or lost to follow-up will be excluded.

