APPENDIX E: SCHEDULEOF ASSESSMENTS

	Pre- Catheterizatio	Device Implan	Follow up within 48 hours	Follow up at 30 ± 7 days	Follow up at 6 ± 1months
Domographia Data		шран	within 40110015	30 ± 7 uays	
Demographic Data	Х				
Physical Exam Data	Х		Х	Х	Х
Medical History					
Data	Х				
Procedure Data		Х			
Device Data		Х			
Transthoracic					
Echocardiogra					
m Data	Х	X *	Х	Х	Х
Adverse Event Data		Х	Х	Х	Х
Death Data		Х	Х	Х	Х
	* optional Intra-procedure Transthoracic Echocardiogram				

APPENDIXF

PROTOCOL DEVIATION REPORTING FORM

Report Date:	Title:	
Sponsor:	Principal Investigator:	
Date of Deviation/ Violation:	Subject Identifier: (if available)	

Reporting Deviations to IRB

*Sites must report violations that affect the safety and welfare of the subject to be submitted within 10 working days from the date the Investigator becomes aware of the event.

- Minor Deviations that do not affect the safety and welfare of the subject may be submitted at the time of continuing review. Please note that the sponsor's requirement may differ from IRB's reporting requirements; contact the sponsor and your institutional IRB to confirm if you have any questions regarding their policy.
- FDA 21 CFR 56.108(a)(4) and ICH 3.3.7 state that planned protocol deviations require prior approval of the IRB except when necessary to eliminate apparent immediate hazards to human subjects. Please submit this form to the CCISC as soon as possible after receiving sponsor approval for the planned deviation and prior to the deviation occurring.

Protocol Deviation/Violation Assessment		
Did the protocol deviation/violation affect the safe of the subject?	Yes* No	
Has the Sponsor been notified of this event?	Yes No	
Will the subject continue his/her participation in	Yes No	
Was the deviation planned or unplanned?	Planned**	Unplanned
(**please provide prior approval of Sponsor)		
Protocol Deviation/Violation Description and	Reason	

Please provide a description of the deviation/violation:

Please explain the reason for the	deviation/violation:	
-----------------------------------	----------------------	--

Corrective Action

Please describe what action(s) you have taken to prevent recurrence of this deviation/violation in the future:

Principal Investigator Signature:

Date:

Protocol Deviation Tracking Log

Tool:	Protocol Deviation Tracking Log				
Purpose:	To record all protocol deviations that occur at a study site				

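### The lost-to-follow-up rule asks for two missed visits in a window that holds one, so the second exclusion ground in Section 7.4 is inoperative or will be read differently by sites

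*Protocol*

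**What the plan says.** **The rule.** Section 6 (Study Completion) deems a subject lost to follow-up "after two missed scheduled visits within the 6month window". After a comma, with no linking word, it adds "a minimum of two unsuccessful phone calls from investigational site personnel to the subject". A certified letter is sent once the subject has been deemed lost.

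**The sentence before it.** The preceding paragraph of Section 6 uses the same window for one visit: "If a subject misses the scheduled follow-up visit within the 6-month window, the subject will be considered as having missed the visit".

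**The schedule.** Appendix E lists three follow-up contacts: within 48 hours, "Follow up at 30 ± 7 days" and "Follow up at 6 ± 1months".

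**Where the status is used.** Section 7.4 restricts the primary and secondary analyses to subjects who leave the laboratory with a device in the duct. It then removes two further groups: those with no follow-up visit up to the six-month window (plus or minus one month), "or lost to follow-up will be excluded". Section 8.2 also ends safety surveillance once a subject is deemed lost.

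**The endpoint that depends on it.** Section 7.2 assesses closure (Grade 0 or 1 shunt) by transthoracic echocardiography (TTE) at the six-month visit, with the Section 7.4 population as denominator. Section 2.1 is looser and accepts follow-up within six months.

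**The concern.** The status decides which implanted subjects leave the safety, effectiveness and obstruction analyses, yet its definition does not fit the visit schedule. Three things are at stake.

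- **Consistency between sites.** Sites assign the status. If they count missed visits differently, or differ on whether the calls are an added condition or an alternative, similar subjects will be excluded at one site and kept at another. That difference is in the data before any analysis starts.
- **Effectiveness.** A subject seen early and not at six months can stay in the denominator without the assessment that the numerator needs.
- **Safety and obstruction.** A subject kept with no observed event counts as event-free although follow-up is incomplete. A subject who had a major event and is later classed as lost is removed together with the event.

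The results are to be set beside those of the earlier studies of the device (Sections 7.1, 7.2 and 7.6), so a shift produced by a definition could be taken for a difference in performance.

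**Working it through.** The protocol gives no figure to reproduce here: 500 is a cap on initial enrolment without a derivation, and no rate of missed visits is stated.

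**Step 1. Count the visits.** Appendix E places one scheduled visit at 6 ± 1 months. The rule needs two.

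**Step 2. Test every attendance pattern.** Three visits, each attended (1) or missed (0), give 2 × 2 × 2 = 8 patterns. The first ground in Section 7.4 is no visit at all. The second is lost to follow-up, tested under two readings of the window and assuming that the two calls failed: narrow (the 6 ± 1 month visit window) and broad (the whole six months of follow-up).

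| 48 h, 1 month, 6 months | No visit at all | Lost, narrow | Lost, broad |
|---|---|---|---|
| 1, 1, 1 | no | no | no |
| 1, 1, 0 | no | no | no |
| 1, 0, 1 | no | no | no |
| 1, 0, 0 | no | no | yes |
| 0, 1, 1 | no | no | no |
| 0, 1, 0 | no | no | yes |
| 0, 0, 1 | no | no | yes |
| 0, 0, 0 | yes | no | yes |

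- Narrow: 0 of 8 patterns can meet the rule, so the second ground never applies.
- Broad: 4 of 8 can meet it, including (0, 0, 1), a subject who did attend at six months.
- The first ground works under either reading and removes 1 of 8.
- Pattern (1, 1, 0), missing only the six-month visit, is excluded under neither reading.

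**Step 3. Illustrate the effect on closure.** Inputs: N = 500 (Section 2); closure of about 99% (Section 7.2), applied to those seen; proportion m who miss only the six-month visit, assumed to be 5%, 10% or 20%.

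Number seen = 500 × (1 − m). Closed = 0.99 × number seen, rounded. Bound = closed / 500, which counts those not seen as failures. Intervals are exact (Clopper-Pearson) 95%.

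| m | Seen | Closed | Missing counted as failure | Among those seen |
|---|---|---|---|---|
| 5% | 475 | 470 | 470/500 = 94.0% (91.5 to 95.9) | 470/475 = 98.9% |
| 10% | 450 | 446 | 446/500 = 89.2% (86.1 to 91.8) | 446/450 = 99.1% |
| 20% | 400 | 396 | 396/500 = 79.2% (75.4 to 82.7) | 396/400 = 99.0% |

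**Step 4. Safety.** Section 7.1 takes both numerator and denominator from the Section 7.4 population. An implanted subject with a major event in the first month who is later classed as lost is therefore absent from both, although the event was observed.

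**The case against.** **The exclusion as a whole does not fail.** A reader might infer that Section 7.4 cannot work as written. That goes too far: subjects without a device, and subjects never seen after the procedure, are excluded without the lost-to-follow-up status. Only the second ground is affected.

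**Two misses may be possible.** The window is two months wide, so the rule could mean a missed appointment and a missed rescheduled one. A subject who never returns would then be lost and excluded. This reading cannot be ruled out, but Appendix E schedules one visit and nothing mentions a rescheduled one. It also classifies pattern (1, 1, 0) the opposite way from the narrow and broad readings, which shows how sites could diverge.

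**The percentages are not the protocol's own result.** A reader might take 94.0%, 89.2% and 79.2% as effectiveness as written. The protocol does not say how a retained subject without a six-month TTE is counted, and under Section 2.1 an earlier TTE might suffice. If all such subjects counted as closed, the rate would be 495/500, 496/500 and 496/500, or 99.0% to 99.2%. The figures are a bound, under the Section 7.2 definition and assumed rates.

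**Missing outcomes belong in the SAP, and nothing is tested.** Handling of missing outcomes may well be in a SAP that is not shown, and Section 7.6 states that there is no formal hypothesis, so no test or success criterion turns on this. Both points stand. They do not remove the problem: the definition is fixed in the protocol and applied by sites, and Section 7.4 itself states that lost subjects leave the safety analysis.

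**Conclusion.** The point holds in limited form. The rule requires two missed visits in a window to which Section 6 and Appendix E assign one, and it leaves open how visits and calls combine. The second exclusion ground in Section 7.4 is therefore inoperative or open to different readings, while the first is sound.

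On the narrow and the broad reading alike, a subject who misses only the six-month visit stays in the analysis population without the TTE that Section 7.2 calls for. Where the status is applied, Section 7.4 discards safety events already observed; that follows from its text whatever the SAP says about missing data.

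The size cannot be known from the protocol. With 5% to 20% missing the last visit and 99% closure among those seen, both assumptions, the missing-as-failure bound lies about 5 to 20 percentage points below the rate among those seen. This should be corrected, but it invalidates no test.

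**What to change.** 1. **Section 6.** Define lost to follow-up as the 6 ± 1 month visit missed and at least two documented unsuccessful calls. State the joining word. Keep the letter as an action that follows the status, not as part of the definition.
2. **Section 7.4.** Align the exclusion with that definition, and do not use the status to remove implanted subjects from the safety and obstruction analyses. Count events observed before loss, and report how many subjects had incomplete follow-up, since those without an observed event may not be event-free.
3. **Effectiveness.** Report closure among subjects with a six-month TTE, with missing-as-failure as a sensitivity bound.

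The cost is a few sentences in Sections 6 and 7.4 and one sensitivity row. No additional visit, test or data field is needed.

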6.1 Subject Death

Subject deaths will be documented and reported to the CCISC PDA Module PI as soon as possible (but no later than 3 business days) after becoming aware of the event via the applicable case report form (CRF) within the PDA module. In the event an autopsy is performed whenever possible data on the histopathology of the Amplatzer Piccolo Occluder device should be submitted within the case report form including any photographs of the gross and microscopic findings.

6.2 Unanticipated Adverse Events

If an unanticipated adverse event occurs, the investigator must notify the CCISC PDA Module PI and the IRB immediately, but no later than 10 working days of the investigator's knowledge of the event, as required by 21 CFR §812.150. CCISC Scientific Committee will perform a Root Cause Analysis (RCA) to investigate the cause of the event, and, as appropriate, will be responsible for notifying FDA and all other participating IRBs and investigators.

6.3 Core Laboratory

A Core Lab will not be used to review and adjudicate patient's clinical information, angiograms and transthoracic echocardiography. However, the CCISC will randomly audit up to ten percent of the patients' data entered in the PDA module from each institution. Service details are previously outlined in the applicable Service Agreement between the CCISC participating site and the CCISC.

6.4 Study Committees

6.4.1 Publication Committee

A Publication Committee may be established to oversee study publications. Publication Committee membership may include the national coordinating investigator, Principal Investigators, a representative of CCISC, and a statistician. The Publication Committee will be responsible for identifying, selecting and approving publication proposals and determining authorship according to a Publication Plan. A Publication Committee charter will define membership of the committee and outline the roles and responsibilities of the committee, as well as rules to define authorship.

6.4.2 Clinical Events Committee (CEC)

An independent CEC will be responsible for providing review and adjudication of pre-defined clinical events, including major and minor complications, deaths, or other events or endpoints as outlined in the CEC Charter. The CEC is responsible for reviewing all reportable Adverse Events as defined in section 5.

The CEC will also advise the site PIs on the continuing validity and scientific merit of the clinical study. CEC members could be investigators in the clinical study. At any time during the study, the CEC may offer opinions or provide formal recommendations concerning aspects of the study that impact subject safety (e.g. safety-related protocol changes or input regarding study-related adverse event rates).

The primary function, responsibilities and membership of the CEC will be described in detail in a CEC charter.

7 STATISTICAL CONSIDERATIONS

The following section describes the statistical methods for the clinical investigation and justification of the clinical study protocol.

7.1 Primary Safety Endpoint

The primary safety endpoint is the rate of major adverse events through up to six-months after an attempted device implant (refer to **Appendix A** for definition).

The proportion of subjects experiencing a major AE through up to six-months will be estimated. The 95% confidence interval for the percent of major AE will be calculated using the exact binomial method. The numerator for the event rate is the number of subjects who experienced an event through up to six-months. The denominator is the number of subjects in the analysis population (As detailed in Section 7.4). The primary safety endpoint rate will be descriptively compared with the rate reported in the Amplatzer Piccolo Occluder IDE and Continued Access Protocol studies. The overall estimated rate for major complications based on published literature ranges between 4.0 to 10.0%.

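### The six-month major-event rate is a crude proportion over a population selected on follow-up, so infants without six-month data are either counted as event-free or dropped, and the net direction of the error is not fixed

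*Protocol*

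**What the plan says.** Section 7.1 names the estimator and the interval: "The proportion of subjects experiencing a major AE through up to six-months will be estimated", and "The 95% confidence interval for the percent of major AE will be calculated using the exact binomial method". The numerator is a count of infants with an event ("The numerator for the event rate is the number of subjects who experienced an event through up to six-months"). The denominator is the Section 7.4 population. No allowance is made for unequal observation time.

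Section 7.4 restricts that population to infants who leave the procedure with a device in the duct, and adds that "subjects who had no follow- up visits up to the six-months +/- one-month window, or lost to follow-up will be excluded".

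Section 6 (Study Completion) treats a missed six-month visit as a missed visit and a protocol deviation. Loss to follow-up needs more: "A subject will be considered 'Lost to Follow-up' after two missed scheduled visits within the 6month window, a minimum of two unsuccessful phone calls".

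Section 4.4 and Appendix E count three follow-up assessments: within 48 hours, one headed "Follow up at 30 ± 7 days", and one at six months plus or minus one month. Appendix A counts only device- or procedure-related events as major, so an unrelated death is not an event.

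**The concern.** The quantity of interest is the risk of a major event over six months. A crude proportion estimates it cleanly only if everyone in the denominator is observed for six months or until an event. Sections 7.1 and 7.4 do not secure this. One group without six-month data stays in as non-events. Another is removed together with whatever had been recorded for it.

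Section 2.1 lists embolization, stenosis and access complications that arise more than 24 hours after the procedure, so some events can fall after an early last visit. Appendix E plans no visit between about day 37 and month five. Section 7.6 states that there is no formal hypothesis, so this rate and its interval are the primary safety result. They are to be set against the IDE and Continued Access rates. If completeness of follow-up differs between the studies, part of any difference reflects follow-up and not the device, and enrolling 500 infants does not reduce that error.

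**Working it through.** The protocol derives no figure on this point, so there is nothing of its own to reproduce. The check has two parts.

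**1. Who is in the denominator (implanted infants, plain reading of Sections 6, 7.4 and 8.2)**

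- Seen at 48 hours and 30 days, six-month visit missed: one missed visit, so not lost. Kept, event-free unless an event is reported.
- Seen only at 48 hours, two calls fail: lost. Excluded.
- Seen only at 48 hours, family reached by phone: the loss criteria are not met. Kept.
- Participation ended early after any visit, without loss: kept.
- Unrelated death after any visit: kept as a non-event.
- Early major event, later declared lost: excluded, and the event goes too.

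For the infants kept alive but unobserved, the unobserved period is treated as event-free, which lowers the rate. Unrelated death lowers it only against the risk that would apply without such deaths. Against a cumulative incidence with death as a competing event, a non-event is the right score. The figures below therefore concern unobserved time only.

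**2. Size**

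Inputs from the protocol: true six-month risk p = 4% and 10% (the literature range in Section 7.1), and n = 500 (Section 2). Inputs assumed, because the protocol does not give them: L, the share of major events after the last contact, and m, the share of infants kept as event-free without later data. Unseen events are assumed unreported, and missingness unrelated to risk.

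*Kept as event-free.* Crude rate = p(1 − L) + pL(1 − m), so bias = −p × L × m.

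- Last seen at 30 days, L = 5–30%, m = 5–20%:
  - p = 4%: from −4 × 0.05 × 0.05 = −0.01 to −4 × 0.30 × 0.20 = −0.24 points (rate 3.99% to 3.76%).
  - p = 10%: from −0.025 to −0.60 points (rate 9.975% to 9.40%).
- 48-hour-only infants also kept, L = 20–50%, m = 5–20%:
  - p = 4%: −0.04 to −0.40 points.
  - p = 10%: −0.10 to −1.0 points.

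*Dropped while still event-free, early events retained.* Rate = [p(1 − L) + pL(1 − m)] / [p(1 − L) + (1 − p(1 − L))(1 − m)], with L = 5–30% and m = 5–20%.

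- p = 4%, L = 5%, m = 20%: (0.038 + 0.0016) / (0.038 + 0.962 × 0.8) = 0.0396 / 0.8076 = 4.90%. The lowest value in the range is 4.14% (L = 30%, m = 5%).
- p = 10%: 10.33% to 12.09%.

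*Dropped with an early event.* One such infant turns 20/500 = 4.00% into 19/499 = 3.81%, and 50/500 = 10.00% into 49/499 = 9.82%.

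*For scale.* The exact 95% interval for 20/500 is 2.46–6.11% (half-width 1.8 points) and for 50/500 is 7.51–12.97% (half-width 2.7 points). The 500 is the number of infants entered. The analysis population will be smaller and the interval somewhat wider.

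**The case against.** A reader might infer that every infant seen only at 48 hours is scored as event-free for six months, and that the rate as a whole is therefore biased downward. The documents do not support that. Such an infant has missed two visits. If the two calls also fail, Section 6 makes the infant lost and Section 7.4 takes the infant out. That exclusion can raise the rate or remove events, so no single direction follows.

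Three further arguments have force.

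- **Wording.** The Section 7.4 phrase "no follow- up visits up to the six-months +/- one-month window" could mean no visit in that window, and the two missed visits in Section 6 could mean two missed appointments for the six-month visit. Either reading would exclude more infants without six-month data. This changes which error applies but leaves a population selected on follow-up.
- **Events outside visits.** Section 8.2 requires related events to be reported throughout participation, and deaths within three business days. Major events under Appendix A are mostly grave enough to surface without a study echocardiogram, and a stenosis seen only on echo need not qualify. The assumed L and m therefore probably overstate the unseen events.
- **Consequence.** The retention bias lies inside the interval half-width, and the comparison is descriptive with no threshold to cross.

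These arguments limit the size and the certainty. They do not supply a rule for the infant who misses only the six-month visit, nor do they justify dropping an infant whose major event is on record. Handling of partial follow-up might be left to an SAP, but here the protocol itself fixes the estimator and the denominator.

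**Conclusion.** The point holds in a limited form. Section 7.1 applies a crude proportion to a population that Section 7.4 selects on follow-up. Infants kept without six-month data push the rate down, by about 0.01 to 0.6 percentage points for those last seen at 30 days and up to about 1 point if 48-hour-only infants are also kept. Exclusion of infants declared lost works upward when they are event-free, and deletes the event when they are not. The net direction depends on who is lost and cannot be settled from the protocol.

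The sizes rest on assumed values of L and m, on no reporting of events outside visits, and on missingness unrelated to risk. Only the 4–10% range and the 500 come from the protocol. The retention effect is likely to be small unless many infants miss the six-month visit and many major events occur late. The change is worth making because the remedy is cheap and this rate is the primary safety result. The flaw does not invalidate the study.

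**What to change.** For the safety endpoint, change Sections 7.1 and 7.4 as follows.

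- Do not exclude implanted infants for incomplete follow-up or loss, and never drop an infant with a recorded major event.
- Make the primary estimate the six-month cumulative incidence of first major event from the procedure date, censored at last safety contact, with unrelated death as a competing event (Aalen–Johansen) and a 95% confidence interval.
- Keep the crude proportion with its exact interval as a supportive analysis, for the descriptive comparison with the IDE and Continued Access rates. State in Sections 6 and 7.4 exactly which infants without a six-month visit enter its denominator.
- Report the number of infants with complete six-month safety follow-up.

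Cost: revised wording, one standard analysis and some added data capture. The procedure date is on the Appendix C form and an onset date on the Appendix G form. The Appendix D form as shown records timing only in categories, so onset and last-contact dates must be added or taken from source records. The estimate assumes that censoring is unrelated to risk, which may be doubtful for infants who are transferred or discharged, and the headline number is slightly less simple to explain.
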